9.7.1.5. Analysis of Efficacy

Summary descriptive statistics will be presented for all study visits at which efficacy data are collected. Efficacy analyses will be presented for the study eye with supportive analyses presented for the non-study eye.

In general, efficacy analyses will be performed using the FAS and the observed data at each Visit for the study eye. Only data prior to rescue therapy will be summarized and imputation strategies for missing data will only consider data prior to rescue therapy. The primary and secondary endpoint analysis will also be performed using the Per Protocol Analysis Set.

For subjects who discontinue the study prior to the Visit 6, data collected using Early Termination eCRFs will not be summarized separately unless the termination occurred on a scheduled visit (within the visit windows of a particular visit).

ANCOVA and longitudinal models for continuous outcomes will be fit using the MIXED procedure. Categorical analyses will be conducted using the FREQ procedure.

9.7.1.5.1. Primary Efficacy Analysis

Primary Estimands: The primary estimands are the treatment differences between VVN539 and vehicle at 8:00 AM, 10:00 AM, and 4:00 PM at each of Days 7, 14, and 21 in the study eye using the FAS. The primary estimands treat subjects as if they do not receive rescue therapy.

Target Population: Subjects with open-angle glaucoma or ocular hypertension that meet the study entry criteria.

Endpoint: Observed IOP measurements at each time point in the study eye.

Treatment Condition(s): Treatment condition is based on the randomized treatment group.

Population-level Summaries: The difference in the mean IOP at the nine time points of interest and their corresponding p-values and 95% confidence intervals.

Intercurrent Events and Strategies to Address Intercurrent Events

- Discontinuation of study therapy with continued participation in the study without receipt of rescue therapy
 - Treatment Policy – no imputation; use observed data
- Receipt of rescue therapy in the study eye
 - Hypothetical Approach – data for visits after the receipt of rescue therapy will be set to missing and will be analyzed assuming missing at random (MAR) using a longitudinal model (mixed model repeated measures, MMRM)
- Missing data without withdrawal or with withdrawal regardless of reason
 - Hypothetical Approach: visits that are missing data will be analyzed assuming MAR using MMRM

Time-matched longitudinal models adjusting for baseline and including a random effect for center will be used to test time-specific superiority comparisons as well as the overall superiority hypothesis using 95% confidence intervals. To claim study success for the primary endpoint based on the model, the two-sided 95% confidence interval estimates of the treatment differences in mean IOP between VVN539 and vehicle must exclude zero for all 9 time points (8AM, 10AM, and 4PM at Visits 4, 5, and 6). Comparisons will be made first between VVN539, 0.04% versus vehicle. If the treatment differences for all 9 time points are statistically significant, testing will proceed to VVN539, 0.02% versus vehicle.

Data from Days 7, 14, and 21 will be analyzed using MMRM with an unstructured covariance assumed for each treatment with treatment, visit, and visit by treatment interaction as a fixed effects, baseline measurement as a covariate, and a random effect for site. If the model fails to converge using this covariance structure, heterogenous Toeplitz, or compound symmetry will be implemented in this order until convergence is reached.

Sample code for the model run separately for 8AM, 10 AM, and 4 PM:

```
PROC MIXED DATA=indata;
  CLASS subject site visit treatment;
  MODEL IOP = baseline visit treatment visit*treatment / solution DDFM=KR;
  REPEATED visit / SUBJECT=subject TYPE=UN group = treatment;
  RANDOM site;
  LSMEANS visit*treatment / slice = visit CL diff;
RUN;
```

Sensitivity analyses include a time-matched last observation carried forward (LOCF) of the last available IOP measurement as well as analysis of covariance (ANCOVA) analyses at each visit with baseline measurement as a covariate. Percent of baseline and percent change from baseline

will also be performed as a sensitivity of the primary analysis. Additional sensitivity analyses will be performed on the PP Analysis Set as necessary.

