3.1 Overall Design of the Study

This is a prospective, parallel-comparison, multi-center, double-masked, randomized, vehicle-controlled dose-response study assessing the safety and ocular hypotensive efficacy of VVN539 in subjects with POAG or OHT. Approximately 60 subjects will be randomized into one of two active treatment arms or a control arm (20 subjects per cohort):

- Arm 1: 0.02% VVN539 ophthalmic solution
- Arm 2: 0.04% VVN539 ophthalmic solution
- Arm 3: VVN539 ophthalmic solution vehicle

Treatment assignments will be masked to VivaVision, study subjects, Investigators, and site staff.

The study involves 6 clinic visits, including screening, baseline, and treatment visits. The study is open to subjects with OHT and POAG who are either treatment-naïve or are already on ocular hypotensive medication. Subjects on ocular hypotensive who meet screening inclusion and do not meet screening exclusion criteria at Visit 1 will discontinue their prior ocular hypotensive medication for up to 35 days before returning to the site for Visit 2 (baseline). Treatment naïve subjects can return for the baseline visit as early as the day after Visit 1. Subjects meeting all baseline inclusion criteria and none of the baseline exclusion criteria will be randomized into one of the study arms and will return to the study site the next day for the first treatment. Three different dosing regimens (once a day [q.d.] in the morning, q.d. in the evening and twice a day [b.i.d.]) will be tested for 7-9 days, each.

Figure 1: Study Treatment

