5.1.2 Dosage and Administration

Eligible subjects will be randomized in a 1:1:1 ratio to receive either 0.02% or 0.04% VVN539 or vehicle control. The IP will be administered as 1 drop either q.d. or b.i.d in the inferior conjunctival fornix in each eye.

The first dose of VVN539 will be administered in clinic after the 8:00AM IOP has been measured at Visit 3. The subjects will then receive the bottle of IP and will self-administer the IP in the morning (suggested timing between 7:00AM and 9:00AM) each day for 5 days. The study site should call the subject the day prior to Visit 4 to remind them to NOT dose in the morning at home on the day of the visit. The last day of q.d. morning dosing will be Visit 4 when subjects will be dosing in clinic after the 8:00AM IOP has been measured.

Starting the day after Visit 4, subjects will self-administer the IP in the evening (suggested timing between 7:00PM and 9:00PM) each day for 6 days. The last q.d. evening dose will be administered in the evening Visit 5 after the last IOP has been measured.

Starting the day after Visit 5, subjects will self-administer the IP b.i.d (suggested timing between 7:00AM and 9:00AM for the morning dose and between 7:00PM and 9:00PM for the evening dose) each day for 6 days. The study site should call the subject the day prior to Visit 6 to remind them to NOT dose in the morning at home on the day of the visit. The last morning dose will be administered in clinic after the 8:00AM IOP dose has been measured. Subjects will return the IP at Visit 6 and will resume their standard of care treatment.

Subjects should be instructed to administer missed doses as soon as possible, as long as it is not administered within 12 hours of the next scheduled dosing during the q.d. dosing periods or not within 4 hours of the next scheduled dosing during the b.i.d dosing period. Missed doses will be recorded as deviations in the electronic case report form (eCRF).

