For analysis of efficacy endpoints, analysis of covariance (ANCOVA) or longitudinal models will model the observed value or change from baseline of each endpoint as the dependent variable with the baseline measurement of the corresponding endpoint as a covariate and treatment group as a main effect. Longitudinal models will include a covariate for visit as well as an interaction term for visit and treatment.

Subgroups

Not applicable.

Multiplicity

Time-matched longitudinal models adjusting for baseline and including a random effect for center will be used to test time-specific superiority comparisons as well as the overall superiority hypothesis using 95% confidence intervals. To claim study success for the primary endpoint based on the model, the two-sided 95% confidence interval estimates of the treatment differences in mean IOP between VVN539 and vehicle must exclude zero for all 9 time points (8AM, 10AM, and 4PM at Visits 4, 5, and 6). No adjustment to the individual confidence intervals is required since all criteria need to be met to claim superiority.

Comparisons will be made first between VVN539, 0.04% versus vehicle. If the treatment differences for all 9 time points are statistically significant, testing will proceed to VVN539, 0.02% versus vehicle.

Missing Data and Outliers

Every attempt will be made to capture all study data. The primary analysis will be analyzed using observed data assuming missing at random (MAR) using a longitudinal model (mixed model repeated measures, MMRM). Sensitivity analyses of the primary endpoint will be performed utilizing time-matched last observation carried forward (LOCF) of the last available IOP measurement.

Safety analyses will use observed data only.

Visit Windows

The nominal visits listed in the CRF will be used in the summaries. In general, unscheduled visits will not be summarized in tables unless otherwise noted.

Missing Dates

Missing dates that occur for prior or concomitant medications or adverse events will be queried for a date. If no date is obtained, the following imputation rules will apply:

- For start dates, if the given year (or year-month) is the same as study drug administration, the start date will be imputed as study drug administration date; otherwise, missing month-day (or day) will be imputed as '01-01' (or '01').

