9.7.2. Determination of Sample Size

With a sample size in each group of 20, the study will have 80% power to detect a difference of 3.0 mmHg between an VVN539 dose compared to vehicle at each diurnal time point assuming a common standard deviation of 3.3 mmHg, $\alpha = 0.05$ (two-tailed).

There is no correction for multiplicity for multiple time points or comparisons for high or low VVN539 doses.

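### The primary MMRM holds the baseline slope equal at Days 7, 14 and 21; a baseline-by-visit term would be a cheap, low-priority safeguard

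*SAP*

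**What the plan says.** SAP 9.7.1.5.1 gives the model as "MODEL IOP = baseline visit treatment visit*treatment / solution DDFM=KR", run once per clock hour, with an "unstructured covariance assumed for each treatment" and a random site effect. Protocol 9.4.2.1 has the same MODEL statement. The general text in SAP 9.7.1 (Strata and Covariates) takes baseline as a covariate and treatment as a main effect, then adds: "Longitudinal models will include a covariate for visit as well as an interaction term for visit and treatment". No baseline-by-visit term appears in either document, and neither gives a reason for a common slope.

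The sensitivity analyses in SAP 9.7.1.5.1 include "analysis of covariance (ANCOVA) analyses at each visit with baseline measurement as a covariate". Because that analysis is fitted visit by visit, each visit has its own slope.

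The visits are not replicates of one condition. Protocol 3.1 describes "Three different dosing regimens (once a day [q.d.] in the morning, q.d. in the evening and twice a day [b.i.d".] tested in turn, and Days 7, 14 and 21 each close one of them. SAP 9.5.3 requires the interval to exclude zero at all nine visit-by-hour points.

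**The concern.** The plan lets the treatment effect, the variances and the correlations change from visit to visit. Only the relation of IOP to its time-matched baseline is held fixed. The regimen, the hours since the last dose and the time since baseline all change between visits, so equal slopes are an assumption that the plan makes without comment.

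If the assumption fails, the fitted slope is a compromise. At a visit whose own slope is far from it, chance baseline imbalance between arms is over- or under-corrected, and the part of the baseline relation left unexplained goes into the residual variance. Since all nine intervals must exclude zero, one affected visit could matter to the success claim.

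**Working it through.** **The plan's own figure.** SAP 9.7.2 states: "With a sample size in each group of 20, the study will have 80% power to detect a difference of 3.0 mmHg", "assuming a common standard deviation of 3.3 mmHg, $\alpha = 0.05$ (two-tailed"). Allocation is equal (Protocol 5.1.2: "Eligible subjects will be randomized in a 1:1:1 ratio").

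- Unadjusted SE of a difference = 3.3 × √(2/20) = 1.04 mmHg.
- A two-sample t-test with 38 df then has 80.0% power for 3.0 mmHg. The stated figure reproduces.

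**Inputs not in the documents (assumed).** Baseline SD 2.8 mmHg (range 2-4), slopes between 0.3 and 0.9, residual between-visit correlation 0.6 (range 0.5-0.7), residual SD 2.7-3.3 mmHg.

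**Formulas (large sample, complete data).** Let b_v be the true slope at visit v, b_c the common slope that the model settles on, SD_x the baseline SD and s_v the residual SD at visit v.

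- Shift in the treatment difference = (b_v − b_c) × baseline imbalance between the arms.
- SE inflation = √(1 + (b_v − b_c)² × SD_x² / s_v²).
- SD of the chance imbalance = 2.8 × √(2/20) = 0.89 mmHg.

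With equal residual SDs, b_c is the average of the slopes. With unequal ones it is pulled towards the visit with the smallest residual SD.

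**Results at Visit 6 (Day 21), baseline SD 2.8, correlation 0.6**

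| Slopes at Days 7/14/21 | Residual SDs | b_c | Deviation | SE inflation |
|---|---|---|---|---|
| 0.6/0.6/0.6 | any | 0.60 | 0 | none |
| 0.7/0.6/0.5 | 2.7 at each visit | 0.60 | −0.10 | 0.5% |
| 0.75/0.60/0.45 | total SD 3.3 at each visit | 0.66 | −0.21 | 1.8% |
| 0.9/0.6/0.3 | 2.7 at each visit | 0.60 | −0.30 | 4.7% |
| 0.9/0.6/0.3 | total SD 3.3 at each visit | 0.84 | −0.54 | 10.8% |

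Worked example, fourth row: √(1 + 0.30² × 2.8² / 2.7²) = √1.097 = 1.047.

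In the last row, holding total SD at 3.3 fixes the residual SDs at √(3.3² − b_v² × 2.8²) = 2.13, 2.84 and 3.19. That is what pulls b_c up to 0.84.

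**Size of the shift.** In the third row a typical imbalance of 0.89 mmHg moves the Visit 6 difference by 0.21 × 0.89 ≈ 0.19 mmHg. In the fourth row it is 0.30 × 0.89 ≈ 0.27 mmHg. Both compare with a design difference of 3.0 mmHg.

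**Power per time point.** With residual SD 3.3 and baseline SD 2-4, 80% becomes 79.4-79.9% for a slope deviation of 0.1, 77.7-79.4% for 0.2 and 75.0-78.7% for 0.3.

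**Simulation with arm-specific unstructured covariance** (20 per arm, baseline SD 3, correlation 0.6, complete data; site effect and Kenward-Roger adjustment left out). Mean SE at Days 7 and 21:

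| Slopes; residual SD | SAP model | With baseline*visit | ANCOVA at each visit |
|---|---|---|---|
| 0.6/0.6/0.6; 3.3 | 1.029, 1.033 | 1.033, 1.035 | 1.037, 1.036 |
| 0.8/0.6/0.4; 3.3 | 1.054, 1.062 | 1.037, 1.046 | 1.043, 1.048 |
| 0.9/0.6/0.3; 2.7 | 0.893, 0.901 | 0.850, 0.851 | 0.848, 0.851 |

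Average estimates agreed across the three methods in every scenario. In the last two rows, the dependence of the Day 7 and Day 21 estimates on realised imbalance was about ±0.2 and ±0.3 mmHg per mmHg under the SAP model, and near zero with the added term.

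**The case against.** Much of the case against stands.

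- **Validity.** A reader might infer that the common slope biases the treatment differences. It does not: treatment is randomised, so the shift averages to zero. In 600 simulated null trials with slopes 0.75/0.60/0.45, coverage by visit was 0.960/0.965/0.945 with the common slope and 0.962/0.962/0.945 with visit slopes. At 0.9/0.6/0.3 it was 0.937/0.937/0.935 against 0.933/0.937/0.937.
- **Comparison with the ANCOVA.** A reader might infer that the primary model is generally less precise than the ANCOVA at each visit. It is not. With slopes 0.7/0.6/0.5 its mean SEs were 1.052/1.044/1.046 against 1.055/1.051/1.048. With 15% assumed dropout and slopes 0.8/0.6/0.4, its Day 21 SE was smaller (1.110 against 1.139), because it uses the earlier visits.
- **Economy.** One slope is not without benefit. It loses to visit-specific slopes only when a visit's slope deviates by more than about 0.04-0.13, and the model already estimates 3 arms × 6 = 18 covariance parameters from about 60 subjects.
- **Existing cover.** The ANCOVA already relaxes the slope constraint. The SAP does not present it as a missing-data check; under Missing Data and Outliers it names LOCF. So the documents do not support saying that the constraint spoils a missing-data check.
- **Mechanism.** Vehicle contains no drug, so slope changes caused by the regimen would arise mainly in the active arms. A baseline-by-visit term shared by all arms captures these only in part.

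None of this makes the added term unsound or costly. With equal slopes it raised the simulated SE by under 0.5% (1.029 to 1.033 at Day 7, for example).

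**Conclusion.** The point holds as a low-priority improvement. The model fixes one baseline slope across three visits under different regimens, and the plan neither justifies nor relaxes this. Where slopes differ, the cost is a shift conditional on chance imbalance, typically 0.2-0.3 mmHg for deviations of 0.2-0.3, and an SE at the affected visit larger by about 0-2% for modest differences, about 5% for large ones with equal residual SDs, and about 10% in the extreme case.

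That extreme case needs the slope to fall from 0.9 to 0.3 within 14 days and the residual SDs to differ sharply, so it is an upper illustration and not an expectation. Every size here rests on assumed slopes, baseline SD and correlation. The documents support neither equal nor unequal slopes. The precision comparison that matters is with the same MMRM plus the added term.

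**What to change.** Add baseline-by-visit to the fixed effects in SAP 9.7.1 (Strata and Covariates), in the text and code of SAP 9.7.1.5.1, and in the secondary models of SAP 9.7.1.5.2:

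`MODEL IOP = baseline visit treatment visit*treatment baseline*visit / solution DDFM=KR;`

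The LSMEANS statement stays as it is. Record the change in SAP 9.8.2, since Protocol 9.4.2.1 has the model without the term. If the sponsor prefers the common slope, one sentence saying why would do.

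The cost is two fixed-effect degrees of freedom per model, some SAP wording, and an SE increase of under about 0.5% if the slopes are truly equal. No new data are needed.

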9.7.1.5.2. Secondary Efficacy Analyses

Analyses of change from baseline in IOP at each time point and of observed and change from baseline in diurnal IOP will be performed in a manner similar to the primary efficacy analysis. Percent of baseline and percent change from baseline of diurnal IOP will also be performed.

9.7.1.6. Analysis of Safety

Safety will be evaluated by AEs, BCVA, slit-lamp biomicroscopy, central corneal thickness, dilated ophthalmoscopy, heart rate and blood pressure, and clinical laboratory tests (blood chemistry, hematology).

The Safety Analysis Set will be used for all safety analyses. All data, including data after rescue, will be summarized as observed and no data imputation will be performed. No statistical treatment group comparisons will be performed, unless otherwise specified. Analyses will be presented by study eye and non-study eye, if applicable.

For by visit summaries, data collected using Early Termination eCRFs will not be summarized unless the termination occurred within the visit windows of a particular visit.

All visits will be included in listings.

9.7.1.6.1. Adverse Events

AEs are coded using MedDRA Version 24.1. Treatment-emergent adverse events (TEAE) are defined as events that start on or after the date of first dose of double-masked study drug up to and including the last dose of double-masked study medication. Ocular AEs are defined as those events for which an eye has been specified (OD, OS, or OU).

Ocular and non-ocular AEs will be summarized separately. Ocular AEs will be presented by study eye and non-study eye and overall (OU) if an event occurs in either eye.

In all summaries of AEs, percentages are calculated based on the number of subjects in each treatment group of the Safety Analysis Set.

Overall summaries of AEs by treatment will include:

- the number of AEs and SAEs reported;
- the number and percentage of subjects who experienced any AE;
- the number and percentage of subjects who experienced any serious adverse event (SAE) and the reason for seriousness;
- the number and percentage of subjects with any AE by worst severity and worst relationship.

The overall summaries of TEAEs will also include:

- the number and percentage of subjects with any TEAEs leading to discontinuation of double-masked study drug;
- the number and percentage of subjects with any TEAEs leading to study termination.

Summaries of the frequency and percentage of subjects with AEs by SOC and preferred term by treatment group will include:

- All AEs by SOC and preferred term;
- All AEs by SOC, preferred term, and maximum severity;
- All AEs by SOC, preferred term, and maximum relationship.

System organ class (SOC) will be sorted alphabetically, and preferred term (PT) within each SOC will be sorted by overall descending order of frequency according to the following rules in order:

1. Descending frequency within VVN539, 0.04%
2. Descending frequency within VVN539, 0.02%
3. Descending frequency within Vehicle;
4. PT in alphabetical order.

Subjects are counted only once for each SOC and PT. In summaries of maximum severity and maximum relationship, subjects with multiple occurrences of events will only be counted once at the maximum severity/relationship per SOC and PT.

Any treatment-emergent AEs that have a missing severity will be presented as severe in the summary table but will be presented with a missing severity in the data listing. Any treatment-emergent AEs that have a missing relationship will be presented as “Related” in the summary table but will be presented with a missing relationship in the data listing.

All AEs are displayed in listings. In addition, separate listings will be provided for:

- Subjects with any treatment-emergent adverse event leading to study drug discontinuation or study termination;
- Subjects with any serious adverse event (treatment-emergent or otherwise);
- Subject deaths.

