2.2.3 Safety Assessments

The safety assessments include:

- Frequency of treatment emergent ocular and systemic adverse events and serious adverse events (SAEs).
- Clinically relevant changes in:
 - Best Corrected Visual Acuity (by Early Treatment Diabetic Retinopathy Study [ETDRS])
 - Slit-lamp Biomicroscopy

- Central corneal thickness
- Ophthalmoscopy (dilated)
- Vital signs (heart rate (HR) and blood pressure (BP))
- Clinical laboratory tests (blood chemistry, hematology)

Data from both eyes will be used for the safety analysis.

3 Study Design

[figure not shown]

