8.2.1 Adverse Events (AEs) and Serious Adverse Events (SAEs)

AEs will be monitored throughout the study. Subjects will be encouraged to report any adverse findings during the study whether or not they are related to IP. These can be collected either in an unsolicited fashion without any prompting or in response to a general question such as: “Have you noticed anything different since you started the study; began the IP, etc?”

All AEs will be captured on the appropriate eCRF. Information to be collected at minimum includes event description, onset, assessment of severity, relationship to IP, and outcome.

The Investigator will record all AEs with start dates occurring any time after informed consent is obtained until 7 (for nonserious AEs) or 30 days (for SAEs) after the last day of study participation. At each study visit, the Investigator will inquire about the occurrence of AE/SAEs since the last visit. Events will be followed for outcome information until resolution or stabilization.

Any medical condition that is present at the time that the subject is screened will be considered as baseline and not reported as an AE. However, if the study subject's condition deteriorates at any time during the study, it will be recorded as an AE.

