9.4.3 Safety Analyses

Safety analyses will be performed on all subjects in the Safety Analysis Set. The assessment of safety will be based on the summary of ocular and non-ocular treatment emergent adverse events (TEAEs), BCVA, central corneal thickness, vital signs, clinical laboratory tests, and ophthalmic exams using slit-

lamp biomicroscopy and dilated ophthalmoscopy. Summaries will be provided by treatment group, and for ocular assessments separately by study-eye and non-study-eye.

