9.4.3.1 Adverse Events

AEs will be coded using MedDRA (most current version) and categorized by system organ class using preferred terms. Separate summaries of AEs related to treatment (as reported by the Investigator) and by severity will be presented. The number of deaths and SAEs will also be presented, and events leading to discontinuation from the study will be listed and tabulated.

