9.5.1.4.1. Adverse Events

AEs will be monitored throughout the study. Subjects will be encouraged to report any adverse findings during the study whether or not they are related to IP. These can be collected either in an unsolicited fashion without any prompting or in response to a general question such as: "Have you noticed anything different since you started the study; began the IP, etc?"

All AEs will be captured on the appropriate eCRF. Information to be collected at minimum includes event description, onset, assessment of severity, relationship to IP, and outcome.

The Investigator will record all AEs with start dates occurring any time after informed consent is obtained until 7 (for nonserious AEs) or 30 days (for SAEs) after the last day of study participation. At each study visit, the Investigator will inquire about the occurrence of AE/SAEs since the last visit. Events will be followed for outcome information until resolution or stabilization.

Any medical condition that is present at the time that the subject is screened will be considered as baseline and not reported as an AE. However, if the study subject's condition deteriorates at any time during the study, it will be recorded as an AE.

An AE is any untoward medical occurrence in a patient or clinical study subject, temporally associated with the use of study intervention, whether or not considered related to the study intervention. An AE can therefore be any unfavorable and unintended sign (including an abnormal laboratory finding), symptom, or disease (new or exacerbated) temporally associated with the use of study intervention.

An AE or suspected adverse reaction is considered "serious" if, in the view of either the Investigator or Sponsor, it results in any of the following outcomes:

- Death,
- A life-threatening AE,
- Inpatient hospitalization or prolongation of existing hospitalization,
- A persistent or significant incapacity or substantial disruption of the ability to conduct normal life functions, or
- A congenital anomaly or birth defect.

Important medical events that may not result in death, be life-threatening, or require hospitalization may be considered serious when, based upon appropriate medical judgment, they may jeopardize the subject and may require medical or surgical intervention to prevent one of the outcomes listed in this definition.

The severity of all AEs will be assessed by the Investigator and graded as follows:

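### The SAP ends the treatment-emergent window at the last dose with no margin, and none of its three by-term adverse event tables isolates treatment-emergent events

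*SAP*

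**What the plan says.** - **Window.** SAP 9.7.1.6.1 opens the TEAE window on the date of first dose and keeps it open "up to and including the last dose of double-masked study medication". No days are added. The protocol gives no TEAE window of its own.
- **Recording.** Protocol 8.2.1: "The Investigator will record all AEs with start dates occurring any time after informed consent is obtained". That section and SAP 9.5.1.4.1 both continue recording "until 7 (for nonserious AEs) or 30 days (for SAEs) after the last day of study participation".
- **Time off drug but in the study.** Under SAP 9.5.1.2.4, rescued subjects stop the product and remain for safety follow-up. SAP 9.7.1.5.1 foresees a second group: "Discontinuation of study therapy with continued participation in the study without receipt of rescue therapy".
- **Discontinuation outputs.** SAP 9.7.1.6.1 counts subjects with TEAEs that lead to drug discontinuation or study termination, and lists them separately. Both outputs are limited to TEAEs. Protocol 9.4.3.1 promises a listing and a tabulation of events leading to study discontinuation, and that sentence carries no such limit.
- **By-term tables.** SAP 9.7.1.6.1 specifies three by system organ class and preferred term. The first is "All AEs by SOC and preferred term". The other two add maximum severity and maximum relationship, also on all AEs.
- **Basis for safety.** Protocol 9.4.3 and the SAP synopsis both state: "The assessment of safety will be based on the summary of ocular and non-ocular treatment emergent adverse events (TEAEs". Protocol 2.2.3 also names treatment-emergent events. Protocol 9.4.3.1 says only AEs: "Separate summaries of AEs related to treatment (as reported by the Investigator) and by severity will be presented".
- **Missing values.** SAP 9.7.1.6.1 sets missing severity to severe and missing relationship to related, but only for treatment-emergent AEs.
- **Declared changes.** SAP 9.8.2 does not mention a move from TEAE to all-AE tables.

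**The concern.** Safety is the secondary objective of this first-in-human trial (Protocol 1.2 and 2.1). A reader will want to know which terms began on or soon after study drug, in which arm, and which events made subjects stop or leave. As specified, the SAP does not answer either question cleanly.

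On the first question, the by-term tables mix pre-dose, on-treatment and later events. Subjects are counted once per term, at maximum severity or relationship. A pre-dose event can therefore hide whether, and how severely, the same term occurred on drug.

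On the second, the dedicated outputs depend on a label that an event loses if it starts after the last dose. Yet an event that makes a subject stop drug can easily start after what turns out to be the last dose.

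**Working it through.** The plan gives no AE rates and no figure on this point, so there is nothing to reproduce. The check follows the stated rules through a case and then counts days.

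**1. One case.** Protocol 5.1.2 suggests evening doses between 7 and 9 PM. Suppose a subject doses on the evening of day d, has an event on the morning of day d+1 and never doses again. The event starts after the last dose whether the window closes by date or by dose, so it is not a TEAE, although it caused the discontinuation. The same holds for an AE during off-drug follow-up that leads a subject to leave the study.

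| Output | Does this event appear? |
|---|---|
| TEAE discontinuation and termination counts (SAP 9.7.1.6.1) | No |
| TEAE discontinuation/termination listing (SAP 9.7.1.6.1) | No |
| All-AE tables and overall AE counts (SAP 9.7.1.6.1) | Yes, not identified as the cause |
| Listing of all AEs; SAE listing if serious | Yes |
| Reasons for study discontinuation (SAP 9.7.1.2) | Reason category only, and only for study exit |

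**2. Days recorded but outside the window.** Inputs:
- First dose on Day 1.
- Visit 6 on Day V = 21 to 23 (schedules in both documents).
- A completer's last dose is at Visit 6 (Protocol 7.1.6).
- Recording margin m = 7 days, or 30 for serious AEs (SAEs).
- Last dose on Day L.

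Recording days after first dose = V + m. Days outside the window = (V − L) + m.

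| Case | Non-serious | SAE |
|---|---|---|
| Completer, L = V = 21 | 7/28 = 25% | 30/51 = 59% |
| Completer, L = V = 23 | 7/30 = 23% | 30/53 = 57% |
| Assumed stop L = 7, followed to Day 21 | (14+7)/28 = 21/28 = 75% | (14+30)/51 = 44/51 = 86% |
| Assumed stop L = 7, followed to Day 23 | (16+7)/30 = 23/30 = 77% | (16+30)/53 = 46/53 = 87% |

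**3. Effect of a tail equal to m.** Days outside become V − L.
- Completer: 0.
- Stop on Day 7, non-serious: 14/28 = 50% to 16/30 = 53%.
- Stop on Day 7, SAE: 14/51 = 27% to 16/53 = 30%.

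**4. Tables.** By-term tables specified: 3. Specified on TEAEs: 0. Consent at Visit 1 (Day −35 to −1) puts 36 to 2 pre-dose calendar days, counting Day 0, inside the recording period that feeds them.

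**5. Missing values.** An AE that starts before the first dose or after the last, with severity or relationship missing, belongs in the all-AE tables but has no rule there.

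**The case against.** **TEAE tables may have been intended.** The SAP introduces the three tables as things the summaries will include, not as a complete list. Its synopsis commits to TEAE summaries, its overall summaries refer to TEAEs, and its missing-value rules speak of treatment-emergent AEs in the summary table. This stands as a plausible account of intent. It does not supply a specified table.

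**Protocol 9.4.3.1 sits under 9.4.3, so its AEs may mean TEAEs.** That is possible. But the protocol sets no window, so it is the SAP's definition that removes the late events from the promised tabulation.

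**Pre-dose noise is small.** This largely stands. The schedules mark AE assessment only from Visit 2, and the visit descriptions list it first at Visit 3. Conditions present at screening are not AEs, biomicroscopy findings become AEs only from Visit 3, and the tables cover dosed subjects only. The AE definition also speaks of temporal association with study treatment. Against this, recording starts at consent and each inquiry looks back to the last visit, so the noise is probably small rather than nil.

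**The percentages count days without assessment.** This stands. No visit follows Visit 6, so a completer's window covers every scheduled treatment visit. The figures are calendar spans only.

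**The relationship table covers the need.** In part. An event can be called related on timing alone, so that table is broad. It still rests on the investigator's judgment and is not a count of all events on or soon after drug.

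**The tail length is a choice.** This stands. The documents require no particular length.

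**Conclusion.** The point holds, and it should be corrected. Followed as written, the SAP undercounts AEs leading to drug discontinuation or study exit whenever such an event starts after the last dose. It also specifies no by-term table that isolates the events on which the protocol and its own synopsis base safety. The size in events is unknown. In calendar days it is 25% to 23% (non-serious) and 59% to 57% (SAE) for completers. It is 75% to 77% and 86% to 87% for a subject assumed to stop on Day 7 and followed to Day 21 to 23.

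Some stronger readings are tempting but not supported:
- **Late events disappear.** They do not. They remain in the all-AE tables, overall counts and listings, and SAEs are listed whether treatment-emergent or not.
- **Pre-dose events bias the arm comparison.** Events before any dose add noise, not bias, and SAP 9.7.1.6 plans no group tests on safety unless otherwise specified.
- **The span runs to Day 27.** Three regimens of up to 9 days each (Protocol 3.1) would give 27 days, but the schedules place Visit 6 no later than Day 23.
- **Visit 6 findings are excluded, or clearly included.** Neither is established. The window opens on a date but closes at a dose, so events later on the last-dose day are unclear. The SAP's rules on imputed dates and on exposure duration do not settle it.

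**What to change.** Amend SAP 9.7.1.6.1 before the mask is broken:

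1. Produce the by-term, maximum-severity and maximum-relationship tables on TEAEs, and show pre-dose AEs separately.
2. End the TEAE window at the date of last dose plus a stated tail within existing collection, for example 7 days for non-serious AEs and 30 for SAEs. State that events on the last-dose date count as TEAEs. Flag events that start after recorded rescue.
3. Tabulate and list every AE after first dose that leads to drug discontinuation or study termination, whether or not it falls in the TEAE window.
4. Apply the missing-severity and missing-relationship rules to every AE in the tables.

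The cost is SAP wording and light programming. Recording already runs 7 or 30 days past the last day of participation, which is never before the last dose, so such a tail needs no new data. Rescue is already annotated in the eCRF, but medication is recorded only through Visit 6 or discontinuation (SAP 9.5.1.2.3), and the flag reaches no further. TEAE counts may rise slightly and include some events that occur on other therapy.
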